## Study Summary

Title	Pulsed ElectroMagnetic Field (PEMF) therapy in Treating Post-Traumatic Stress Disorder (PTSD) & Trauma
Methodology	Single arm observing treatment intervention; no control, no placebo/sham
Study Duration	Estimated duration for the main protocol (the start and end of the treatment programme) is approximately 3 weeks
Study Centre(s)	Private clinic in Bristol, U.K.
Objectives	
Primary Objective: To evaluate the efficacy of Artificial Intelligence (AI) guided software rendering PEMF treatment to treat PTSD & Trauma
 
Secondary Objective: To evaluate the feasibility of AI implementation in drastically reducing the time required to train PEMF therapists, thereby allowing faster adoption of PEMF therapy into mainstream practice through use by other licensed/regulated/trained healthcare professionals such as talking therapists, nurses, doctors, social workers, and carers

Number of Actual Participants	5
Diagnosis and Main Inclusion Criteria	
Inclusion Criteria:
 
 
• Aged 18 or over
 
• Have been diagnosed with PTSD or Trauma
 
• Have been experiencing on-going, continuous symptoms of PTSD or Trauma for at least the past 6 months
 
• Can attend 6 sessions lasting 90 minutes over 3 weeks
 
• Consent and Compliance with all requirements of clinical trial, including dissemination of results, with anonymity of identity provided
 
 
Exclusion Criteria:
 
 
• Under the age of 18 years old
 
• Have not been diagnosed with PTSD or Trauma
 
• Have serious health conditions such as cancer
 
• Unable to attend 6 sessions
 

Study Product, Dose, Route, Regimen	Treatment group will receive 6 sessions, each lasting 1.5 hours of PEMF treatment over the course of 3 weeks through the CE-marked CIO devices

	classified by the U.S. Food & Drug Administration as a Type 11a Medical Device. SCIO devices contain a frequency generator and scanning technology, along with electrode harnesses that connect to the forehead, wrists, and ankles. The devices are controlled by software that is guided by A.I.
Statistical Methodology	Primary Endpoint: Symptoms of PTSD & Trauma are evaluated through a questionnaire, with scale ratings for different symptoms. Symptoms were correlated with information available on the NHS website.

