**Goals of the Study:**

1. To evaluate the efficacy of Pulsed Electromagnetic Therapy in the treatment of PTSD and Trauma. The goal of the trial is to improve the symptoms of the patients and alleviate PTSD-related issues they may have.

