## **Methods:**

### **Study Design:**

Single-arm study involving five (5) subjects undergoing 6 90-minute sessions of Pulsed Electromagnetic Therapy. All patients received the same treatment. Harnesses were placed on the head, wrists, and ankles of the body to conduct the electromagnetic frequencies. Patients were encouraged to rest and relax whilst the therapy was conducted, as it does not require any tasks by the patient. Patients were required to complete a questionnaire before and after the trial. This questionnaire enquired about the different symptoms related to PTSD and Trauma, and asked patients to rate their symptoms on a scale. These questionnaires would form the foundation of the study's findings, as it would give a clear comparison of symptoms before and after the trial.

All aspects of the trial were exempt from a U.K. ethics committee board review because the trial was a non-invasive method of treatment, did not collect and tissue or fluid samples and the device is CE-marked and had been used in other trials previously approved and published on Clinical Trials.gov. Documents were provided on clinicaltrials.gov as evidence of this exemption.

All patients were from the inclusion criteria, and any patients exhibiting cases from our exclusion list were rejected from the pilot study. Patients were recruited through the National Centre for Electromagnetic Therapy social media pages, including Facebook, Instagram, and [www.ncet.co.uk](http://www.ncet.co.uk).

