### **Clinical Trial Outline**

**Prior to Trial** – Selected patients are required to fill out questionnaire provided to them by NCET.

**Week 1** – All patients receive two hours' worth of PEMF treatment across two separate sessions.

**Week 2** – All patients receive two hours' worth of PEMF treatment across two separate sessions.

**Week 3** – All patients receive two hours' worth of PEMF treatment across two separate sessions.

**Week 4** – All patients are required to fill out questionnaire provided to them by NCET. Dissemination of study and findings published.

Whilst the clinical trial is short in length, the ability for patients to get in contact with NCET is always available. Contact can be maintained between the patient and company regarding their lives after the trial. Information provided by patients after the trial has finished will be considered in the trials' findings.

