## Results & Findings

### **Prior to the Trial**

Once participants had been screened and approved for clinical trial study, they were required to fill out a questionnaire that sought to establish the specific issues that they were experiencing due to PTSD and Trauma. These responses were weighted as an average and are provided below.

For clarification, a rating of one (1) on the scale indicates a very severe case of a specific symptom, five (5) means a frequent feeling of a symptom, and ten (10) indicates that the symptom is not experienced at all. A weighted average score has been chosen as a foundation for our results, to compare them more accurately before and after the trial. However, specific notes and observations shall be included where needed.

Statements were also used, whereupon a patient would respond with either Daily (3 or more times a week), Weekly (2 to 3 times a week), Monthly (3 to 4 times a month), or Rarely (Once every 3 months or longer).

Question	Average Score
Have you experienced or witnessed a life-changing event that caused intense fear, hopelessness or horror?	All patients recorded 'Yes'.
Have you experienced either repeating dreams, flashbacks, or intense physical/emotional stress that relate back to the	Daily – 1 Patient Monthly – 2 Patients Rarely – 2 Patients

traumatic event(s)?	
Do you avoid thoughts, feelings, actions, conversations, or people related to the event?	Daily – 1 Patient Weekly – 2 Patients Monthly – 1 Patient Rarely – 1 Patient
Have you felt detached or negative towards yourself or others since the traumatic event(s) happened?	Daily – 4 Patients Monthly – 1 Patient
Do you have problems sleeping?	Daily – 1 Patient Weekly – 2 Patients Rarely – 2 Patients
Do you become increasingly irritable, angry, or engage in self-destructive behaviour?	Daily – 1 Patient Monthly – 3 Patients Rarely – 1 Patient
How long have your symptoms persisted?	Longer Than Three Years – 3 Patients Longer Than A Year – 1 Patient 8-12 Months – 1 Patient
Do you experience heightened version of anxiety, sensitivity, or depression?	Daily – 3 Patients Weekly – 1 Patient Monthly – 1 Patient
Rate Your Quality of Life	Average Score: 6
Rate The Severity of Depression	Average Score: 6.4
Rate How Difficult It Is To Fall Asleep	Average Score: 5.6
Rate The Severity of Flashbacks Relating to a Traumatic Event	Average Score: 5
Rate The Severity of Headaches or 'Brain Fog'	Average Score: 4.6
Rate The Severity of Fatigue	Average Score: 5

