### **During The Trial**

There were no changes to the initial plan for the clinical trial. All patients attended their arranged appointments and reported no negative side effects to the treatment.

The Lead Practitioner noted valuable verbal feedback during sessions with each patient.

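### The only scored endpoint is a questionnaire with no stated validation whose reported ratings are mostly not specific to PTSD, so the conclusion about PTSD goes beyond what was measured

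*Combined protocol and SAP*

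**What the plan says.** The aim under Goals of the Study is "To evaluate the efficacy of Pulsed Electromagnetic Therapy in the treatment of PTSD and Trauma". In the Study Summary (Statistical Methodology) the primary endpoint reads: "Symptoms of PTSD & Trauma are evaluated through a questionnaire, with scale ratings for different symptoms". The next sentence gives the only stated basis for the content: "Symptoms were correlated with information available on the NHS website".

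The Clinical Trial Outline says who supplies the form: "Selected patients are required to fill out questionnaire provided to them by NCET". Methods, Study Design, gives its weight: "These questionnaires would form the foundation of the study's findings, as it would give a clear comparison of symptoms before and after the trial". The other efficacy information is unscored. During The Trial reports, for example: "The Lead Practitioner noted valuable verbal feedback during sessions with each patient".

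Prior to the Trial sets out two kinds of item: frequency questions (Daily, Weekly, Monthly, Rarely) and ratings anchored at 1, 5 and 10. On the low anchor it says "a rating of one (1) on the scale indicates a very severe case of a specific symptom"; 5 stands for a frequent feeling and 10 for absence of the symptom.

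After The Trial says patients completed the same form again. Its table holds the exposure question and 11 ratings, and illustrations 2.1 to 2.11 show those 11 ratings. The closing statement, just before the Endnotes, declares the primary objective met for PTSD symptoms and presents the therapy as a beneficial alternative to prescribed drugs.

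**The concern.** An efficacy claim about PTSD needs a measure whose score is known to track PTSD severity, with some idea of how large a change exceeds measurement error and matters to patients. Neither is stated. Expected Outcomes anticipates a marginal improvement in every patient but does not say how many points that is. No item or sum is named as primary, so any of the 11 ratings can be put forward as the result.

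Two things are at stake. A rise of about two points on such an item cannot be translated into a change in PTSD severity, yet the closing statement makes that step. And the sponsor plans a similar, larger study, while the improvements listed under Reflections and Considerations (more patients, control and sham groups, wider spacing of sessions) do not include the outcome measure. The weakness would carry forward.

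**Working it through.** **Step 1: reproduce the reported changes.** Inputs are the item means in the Prior to the Trial and After The Trial tables. Change = after − before.

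| Rating | Before | After | Change | Stated |
|---|---|---|---|---|
| Quality of life | 6.0 | 8.0 | 2.0 | 2 |
| Depression | 6.4 | 6.4 | 0 | none |
| Falling asleep | 5.6 | 8.2 | 2.6 | 2.6 |
| Flashbacks | 5.0 | 7.4 | 2.4 | 2.4 |
| Headaches / brain fog | 4.6 | 6.0 | 1.4 | 1.4 |
| Fatigue | 5.0 | 6.8 | 1.8 | 1.8 |
| Anger | 4.8 | 7.4 | 2.6 | 2.6 |
| Daily tasks | 5.8 | 7.4 | 1.6 | 1.6 |
| Anxiety | 6.2 | 7.0 | 0.8 | 0.8 |
| Happiness | 6.2 | 8.2 | 2.0 | 2 |
| Satisfaction / fulfilment | 5.8 | 7.8 | 2.0 | 2 |

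All 11 agree. Each mean times 5 is a whole number, as it should be with five responses. The changes sum to 19.2, or 19.2 / 11 = 1.75 points per item. No SD, interval or test accompanies them.

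**Step 2: count the items that are not specific to PTSD.** The answer depends on the definition, so three are shown.

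| Items credited as PTSD-specific | Not specific | Change carried by the rest |
|---|---|---|
| Flashbacks only (names the trauma) | 10 of 11 = 91% | 19.2 − 2.4 = 16.8; 16.8 / 19.2 = 87.5% |
| Plus falling asleep and anger | 8 of 11 = 73% | 19.2 − 7.6 = 11.6; 11.6 / 19.2 = 60% |
| Plus anxiety | 7 of 11 = 64% | 19.2 − 8.4 = 10.8; 10.8 / 19.2 = 56% |

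The non-specific items are the majority under each definition, by count and by share of change. The sum only shows where the change lies; the document defines no total score.

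**Step 3: compare the two tables for content.** Six frequency items in the baseline table (re-experiencing, avoidance, detachment, sleep problems, irritability, heightened anxiety) have no result in the post-trial table or in illustrations 2.1 to 2.11. Re-experiencing, sleep, irritability and anxiety have at least a related rating among the 11. Avoidance and detachment have none. Detachment was the item most often marked Daily at baseline (4 of 5 patients), so its course is not reported at all.

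**Step 4: check the response scales.** Daily (three or more times a week) and Weekly (two to three times) overlap at three. The rating anchors mix severity, frequency and absence. They are worded for symptoms and do not fit quality of life, happiness or fulfilment, which contribute 3 × 2.0 = 6.0 of the 19.2 points (31%). Scoring those three as improvements assumes that patients read a high number as good, which the stated anchors do not say.

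**The case against.** **Several general-sounding items are relevant to PTSD.** Sleep, anger and anxiety all appear in the document's own baseline questions about the disorder. This stands, and it is why a range is given. A reader might take one item in 11 (9%) as the PTSD content; that is only the narrowest count. Depression shares a baseline question with anxiety. Crediting it too would leave 6 of 11 (55%) not specific, and the 10.8 points would not move because its change was zero.

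**The data are not silent on PTSD.** Flashbacks rose by 2.4 points, one of the larger changes. This also stands. But it is one self-rating in five patients, with no SD and no comparison group.

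**The form's origin is not known.** A reader might infer that the centre wrote the questionnaire itself and took its items from a website. The text says only that symptoms were correlated with NHS information and that the centre supplied the form. Authorship is not stated.

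**The missing frequency items may have been collected.** A reader might infer that they were dropped or withheld. The documents do not settle this: the form is said to be the same, and the results are absent. The 11 ratings are therefore a count of what was reported, not of everything the form covers.

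**The questionnaire is not the only reason the claim fails.** With five patients, one arm and no sham, a validated scale would be open to the same explanations, including the rest and relaxation that the Discussion itself suggests. This stands in full. The measurement problem is separate: a control group would not make these ratings a measure of PTSD severity.

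**The report is partly cautious.** It refers to symptoms and says the results do not represent the whole UK. That caution concerns generalisation, not what was measured, and it sits beside the claim of an alternative to medication.

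**Conclusion.** The concern holds in a bounded form. The primary endpoint is an unnamed, centre-supplied questionnaire with no stated validation, total score, primary item or threshold for meaningful change. Between 64% and 91% of the ratings reported at both times are not specific to PTSD, and they carry 56% to 88% of the summed mean change. Six trauma-related frequency items lack a reported post-trial result. The closing conclusion on PTSD symptoms and on medication goes beyond this evidence.

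The range rests on which items a reader credits; the majority does not. The reading also rests on the text available for review, which does not include the individual patient statements mentioned in the Discussion and in Reflections and Considerations. A reader might go further and infer that the therapy had no effect on PTSD, or that a better questionnaire alone would have established one. The documents support neither: without a control or patient-level data, the effect is undetermined in both directions. No corrected effect estimate can be calculated.

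**What to change.** **For this report (rewording only):**
- State the endpoint and conclusion as uncontrolled before-after change in self-rated items on an unvalidated questionnaire in five patients, with mean changes from 0 to 2.6 points.
- Remove the statements that efficacy in PTSD was shown and that the therapy is an alternative to medication.
- Report the six frequency items after treatment, or state that they were not collected and correct the sentence saying that the same form was used.

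**For any further use of this protocol:** make the total score of an established, validated self-report PTSD symptom scale the single primary endpoint, at the same two time points. Name the scale and its scoring in advance, with the change regarded as meaningful. Keep the 11 ratings as secondary.

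**Cost:** editing time now; later, one short self-completed form at two existing contacts, so a few minutes per patient. The new primary result will not be directly comparable with the present data, although keeping the 11 ratings preserves a link. This change does not replace the control and sham groups that the report already recommends.

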**Purpose:**

The primary objective is to evaluate the efficacy of Pulsed Electromagnetic Therapy in the treatment of patients who have been suffering from PTSD & Trauma. This will be evaluated using a SCIO device over the course of 6 one-hour sessions.

**Background:**

PTSD and Trauma is often developed after a traumatic experience. These experiences can range from sexual assault, war, health problems, childbirth, or road accidents. PTSD and Trauma is estimated to [affect 3% of the U.K. adult population](#), with a tendency for women to have more of a lifetime prevalence (10-11%) as compared to men (5%). It is unclear why some individuals develop PTSD after traumatic events compared to those who do not.

Treatment for PTSD and Trauma available through the [NHS](#) include Cognitive Behavioural Therapy (CBT) or medication, including citalopram, paroxetine, sertraline, or phenelzine.

**Goals of the Study:**

1. To evaluate the efficacy of Pulsed Electromagnetic Therapy in the treatment of PTSD and Trauma. The goal of the trial is to improve the symptoms of the patients and alleviate PTSD-related issues they may have.

**Duration of the Study:**

The study is estimated to take place over 3 weeks, with enrolment remaining open until the trial starts. A questionnaire is required to be answered before the first session and after the final session of the clinical trial.

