### **Potential Benefits and Risks to Patients**

Every effort is taken to ensure that screening and production of the clinical trial follows a code of ethics. Patients are not at risk of contracting harmful diseases, ailments, or any other negative symptoms. The trial is held in a COVID-19 safe environment, with regular cleaning, monitoring, and health checks performed regularly by staff.

Patient and staff safety is a priority of the clinical trial. To ensure this, potential patients were screened and interviewed in advance of the trial to ensure that they fit the correct profile for the study. They were asked about their medical history, and the accessibility of the clinical trial location in relation to their home. The clinical trial timeframe was agreed upon with all patients to ensure they arrived at their session at the correct time. Patients had the option to drop out of the clinical trial at any point.

There have been no recorded negative side effects to Pulsed Electromagnetic Therapy in the treatment of patients. In the clinical experience of the Investigator, approximately 1% of patients have reported experiencing headaches or dizziness during and/or immediately after a session using the SCIO device. This side effect was not reported to be severe and did not last longer than 12 hours.

Therefore, it is prudent to assume that there will not be any negative health side effects from this clinical trial. Patients were made aware of this potential side effect prior to the trial.

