### After The Trial

Once the trial had been completed over the course of 3 weeks, patients were asked to complete the same questionnaire that was sent out prior to the clinical trial. In the table below, responses have been recorded as an average, with a percentage comparison of improvement or decline in symptoms.

Question	Average Score
Have you experienced or witnessed a life-changing event that caused intense fear, hopelessness or horror?	All patients recorded 'Yes'.
Rate Your Quality of Life	Average Score: 8 ( Improvement of >2 points )
Rate The Severity of Depression	Average Score: 6.4 ( No change )
Rate How Difficult It Is To Fall Asleep	Average Score: 8.2 ( Improvement of >2.6 points )
Rate The Severity of Flashbacks Relating to a Traumatic Event	Average Score: 7.4 ( Improvement of >2.4 points )
Rate The Severity of Headaches or 'Brain Fog'	Average Score: 6 ( Improvement of >1.4 points )
Rate The Severity of Fatigue	Average Score: 6.8 ( Improvement of >1.8 points )
Rate The Severity of Anger or Irritable Outbursts	Average Score: 7.4 ( Improvement of >2.6 points )

Rate How Difficult It Is To Complete Daily Tasks	Average Score: 7.4 ( Improvement of >1.6 points )
Rate The Severity of Your Anxiety	Average Score: 7 ( Improvement of >0.8 points )
Rate Your Level of Overall Happiness	Average Score: 8.2 ( Improvement of >2 points )
Rate Your Level of Satisfaction and Fulfilment In Life	Average Score: 7.8 ( Improvement of >2 points )

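### No systematic side-effect collection is described, so the report of no side effects is not a measured zero, and it must be reconciled with the tiredness reported elsewhere

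*Combined protocol and SAP*

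**What the plan says.** **Scheduled collection.** Duration of the Study sets two time points: "A questionnaire is required to be answered before the first session and after the final session of the clinical trial". Study Design describes the same before-and-after form. Clinical Trial Outline puts the second one in Week 4, after the three treatment weeks: "All patients are required to fill out questionnaire provided to them by NCET. Dissemination of study and findings published".

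**Expected side effect.** Potential Benefits and Risks to Patients reports, from the investigator's clinical experience, that "approximately 1% of patients have reported experiencing headaches or dizziness during and/or immediately after a session using the SCIO device". It adds: "This side effect was not reported to be severe and did not last longer than 12 hours". Expected Outcomes names the same two complaints as the only anticipated reactions.

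**What the form asks.** The tables under Prior to the Trial and After The Trial, and the survey items under Illustrations, list no question on dizziness or on side effects. Headache appears in one rated item, "Rate The Severity of Headaches or 'Brain Fog", combined with brain fog and reported as a five-patient mean.

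**Other channels.** During The Trial says: "The Lead Practitioner noted valuable verbal feedback during sessions with each patient". Expected Outcomes says patients can reach a named contact during the trial. Clinical Trial Outline accepts information that patients give after it.

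**Reported result.** During The Trial states: "All patients attended their arranged appointments and reported no negative side effects to the treatment". Reflections and Considerations reports that patients found two sessions a week tiring, and names exhaustion as a risk.

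**The concern.** The documents expect a short-lived effect tied to individual sessions, but the scheduled instrument is tied to the start and end of the whole programme. No adverse-event definition, standard question, recording form or follow-up window after a session is described. A reader of the safety sentence cannot tell whether patients were asked and said no, or whether nothing was asked.

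Two things depend on it. The closing paragraphs of Reflections and Considerations present the therapy as a beneficial alternative to prescription medication and say no worsening was recorded. Reason For Withdrawal lists unacceptable or unexpected risk as a ground for ending the trial, yet no described process would routinely supply that information.

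**Working it through.** There is no sample size, power or event target to reproduce. The checks are a count of collection points, the arithmetic of the one related item, and exact binomial limits.

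**1. Post-session periods against scheduled instruments**
- Inputs: 5 patients and 6 sessions (Study Design); form before session 1 and after session 6 (Duration of the Study); effect lasting at most 12 hours (risk section).
- Post-session periods: 5 × 6 = 30.
- After sessions 1 to 5: 5 × 5 = 25, with no scheduled instrument; 25/30 = 83.3%.
- After session 6: 5 periods; 5/30 = 16.7%. The final form can fall within these only if completed within 12 hours of the last session. If completed in Week 4, as the outline says, it most likely covers none.

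**2. The headache item**
- Before 4.6, after 6, where 10 means not experienced: 6 − 4.6 = 1.4, which agrees with the stated change.
- The item has no stated recall period and no link to a session. A headache after a session may or may not have affected the rating. If it did, it cannot be separated from a baseline symptom or from brain fog.
- One point on one patient's rating moves the five-patient mean by 1/5 = 0.2.

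**3. Tiredness, passages side by side**
- During The Trial: no negative side effects reported.
- Reflections and Considerations: patients found the twice-weekly sessions tiring, and exhaustion is named as a risk.
- The fatigue rating rose from 5 to 6.8: 6.8 − 5 = 1.8, an improvement. A before-and-after mean can improve while a session-linked complaint is reported elsewhere, so the efficacy ratings cannot stand in for side-effect reporting.

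**4. What a zero could show with this sample**
- Chance of at least one case if the true rate is 1% of patients: 1 − 0.99^5 = 0.049. Zero is expected 95.1% of the time.
- Upper 95% bound for 0 of 5: two-sided 1 − 0.025^(1/5) = 52.2%; one-sided 1 − 0.05^(1/5) = 45.1%.
- If the 1% is instead read per session, with 30 independent sessions (an assumption; the text says patients): chance of at least one = 1 − 0.99^30 = 26.0%; two-sided upper bound for 0 of 30 = 1 − 0.025^(1/30) = 11.6%.

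**The case against.** A reader might infer that the expected effect falls outside every point at which information was gathered. The documents do not support that. Onset can be during a session, when the practitioner was noting feedback. Patients could use a contact during the trial. They also returned twice a week, so complaints after sessions 1 to 5 could have been recalled at the next visit, and the form does contain a headache item. These channels stand. What they lack is a standard question, a record and a time window.

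A reader might also infer that patients were never asked, so that the result rests only on what they volunteered. The text says only that they reported none; it does not say whether anyone asked. The Discussion and Reflections and Considerations point to individual patient statements that were not in the text available for this review, and nothing is inferred from their absence.

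Comparing hours spent in sessions with the 12-hour periods would not help either. That is a share of time, not a chance of detection, and 12 hours is a stated maximum.

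The strongest objection is that little is lost with five patients. At the documents' own 1%, zero cases is the likely result under perfect collection, and the bound on 0 of 5 is very wide. This stands as a limit on what the fix can achieve. It does not rescue the safety sentence, which gives the reader neither the method of enquiry nor that limit.

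**Conclusion.** The concern holds in this form: no systematic side-effect collection is described in the available text, and the questionnaires leave at least 25 of 30 post-session periods without a scheduled instrument. The statement of no negative side effects therefore cannot be read as a measured zero. It also sits in unresolved tension with the tiredness in Reflections and Considerations, and the two passages must be reconciled.

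The count of 25 rests only on the stated number of patients, number of sessions and questionnaire timing. The 52% bound assumes that patients are independent and takes the patient as the unit. The documents do not show that side effects occurred and went unrecorded, and this point does not claim it. Better collection would make a zero interpretable, but five patients could not estimate a 1% rate.

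**What to change.** **For the larger study that the sponsor plans.** At the start of sessions 2 to 6, and on the Week 4 form, have existing staff ask one standard question about headache, dizziness, tiredness and any other new complaint since the previous session. Record yes or no, duration and severity. Report the numbers of patients and of sessions affected, separately from the combined headache and brain fog efficacy rating.

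**For the completed trial.** Unless the sponsor can document how patients were asked, restate the sentence in During The Trial along these lines: *no negative side effects were reported; no systematic enquiry after sessions is described*. Mention the tiredness in the same place, and state that 0 of 5 has a two-sided 95% upper bound of about 52%.

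**Cost.** About one minute per session and a few lines on the form in a further study; for this trial, only rewording. The safety result may look less favourable.
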